13.2 Adverse Events

All AE summaries will be restricted to treatment-emergent AEs (TEAEs), which are defined as those AEs that occurred after dosing and those existing AEs that worsened after start of dosing. If it cannot be determined whether the AE is treatment-emergent due to a partial onset date, then it will be counted as such. Verbatim terms in the eSource forms will be mapped to preferred terms and system organ classes using the Medical Dictionary for Regulatory Activities (MedDRA) (version 23.0).

Each AE summary will be displayed by treatment group. Summaries that are displayed by system organ class and preferred terms will be ordered by descending subject count in the total column by system organ class and preferred term. Summaries of the following types will be presented:

- Overall summary of TEAEs.
- Subject incidence of TEAEs and total number of unique TEAEs by MedDRA system organ class and preferred term.
- Subject incidence of TEAEs of special interest and total number of unique TEAEs by MedDRA system organ class and preferred term.
- Subject incidence of treatment-related TEAEs and total number of unique TEAEs by MedDRA system organ class and preferred term.
- Subject incidence of serious TEAEs and total number of unique serious TEAEs by MedDRA system organ class and preferred term.

- Subject incidence of TEAEs leading to study discontinuation and total number of unique TEAEs leading to study discontinuation by MedDRA system organ class and preferred term.

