Abbreviations: ALP = alkaline phosphatase; BP = blood pressure; ECG = electrocardiogram; eDiary = electronic diary; EOS = End of Study; EOT = End of Treatment; ET = Early Termination; E2 = estradiol; FSH = Follicle Stimulating Hormone; HDL-C = high density lipoprotein – cholesterol; HF = hot flash; HFRDIS = Hot Flash Related Daily Interference Scale; HIV = human immunodeficiency virus; INR = international normalized ratio; ISI = Insomnia Severity Index; LDL-C = low density lipoprotein – cholesterol; LFT = liver function test; LH = luteinizing hormone; PK = pharmacokinetic; PT = prothrombin time; SHBG = sex hormone binding globulin; VMS = vasomotor symptoms.

Footnotes are on the following page.

-  Participants who discontinue study treatment and/or the study prior to the scheduled EOT Visit on Day 28 should attend an Early Termination Visit. The procedures at this Early Termination Visit will be the same as those specified for EOT.
-  The Run-In visit may be conducted by phone. During Treatment and Follow-up Period, Day 7, 14, and/or Day 42 (EOS) visits may be conducted either in-clinic or at home.
-  Clinical breast examination will be performed only at Screening. Gynecological examination to be performed at Screening and Day 28 (EOT).
-  Height will be measured at Screening only.
-  Drugs of abuse panel (see [Appendix 4](#)).
-  Vital signs (supine BP and heart rate, and aural body temperature); vital signs should be taken after the subject has been resting for at least 5 minutes. BP assessment for eligibility must be based on the median of a total of 4 to 6 readings, based on 2-3 readings from two different occasions.
-  Total Cholesterol, HDL-C, LDL-C, triglycerides, and fasted glucose will only be collected at Screening and Day 28 (EOT). PT/INR will only be collected at Screening.
-  Testing for presence of virus (SARS-CoV-2) at Screening, Baseline (Day 1), Days 14, 28 (EOT), and 42 (EOS). COVID-19 antibody testing only at Screening, EOT, and EOS.
-  At the discretion of the Sponsor, other analyses including but not limited to hormone assessments may be performed.
-  FSH level to confirm eligibility. All postmenopausal women must have a serum FSH >40 mIU/mL at Screening.

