9. STUDY POPULATION

9.1 Subject Disposition

Subject disposition information will be summarized for all subjects by treatment group. Summaries will include: the number of subjects screened under protocol Version 2.0 and 2.1, the number of enrolled (randomized) subjects, the number of subjects in the safety population, the number of subjects discontinuing the study, and the primary reason for discontinuation.

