13.1 Extent of Exposure

Study drug exposure based on expected exposure will be summarized by treatment group. Expected exposure will be derived as follows:

- Subjects who complete the Day 28/EOT visit: $(64 \text{ tablets dispensed} - \text{number tablets returned} - \text{number tablets lost}) / (2*28)$
- Subjects who prematurely discontinue prior to Day 28/EOT: $(64 \text{ tablets dispensed} - \text{number tablets returned} - \text{number tablets lost}) / 2*(12FEB2021 - \text{date of first dose} + 1)$

Note: 12FEB2021 is the date of sponsor notification of sites of study termination for safety reasons.

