14. CHANGES TO PROTOCOL-SPECIFIED ANALYSES

Based on the DMC meeting on Thursday Feb 11th and a subsequent internal company meeting, Sojournix terminated the SJX-653-006 study early. At the time of termination, sites were

informed to stop screening and withdraw all subjects from the study. Subjects on treatment were notified to stop dosing immediately.

Due to limited number of randomized subjects, select safety data will be summarized as outlined in Section 13. Efficacy data will not be summarized or tabulated.

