APPENDIX C: LIST OF TABLES, LISTINGS, AND FIGURES

The following proposal for section 14 and 16.2 is completed according to ICH E3 guidelines. The ICH heading numbers and description are in **bold**. Minor changes from this planned index do not need to be amended in the SAP.

TABLES, FIGURES AND LISTINGS

Index of Section 14

| Table Number | Table Title | Analysis Set |
|---------------|--|-------------------|
| 14 | Tables and Figures Referred to but not Included in the Text | |
| 14.1 | Demographic Data | |
| 14.1.1 | Subject Disposition | |
| 14.1.2 | Summary of Demographic and Baseline Characteristics | Safety Population |
| 14.1.3 | Summary of Protocol Deviations Due to COVID-19 | Safety Population |
| 14.3 | Safety Data | |
| 14.3.1 | Displays of Adverse Events | |
| 14.3.1.1 | Overall Summary of Treatment-Emergent Adverse Events | Safety Population |
| 14.3.1.2 | Treatment-emergent Adverse Events by System Organ Class and Preferred Term in Descending Frequency | Safety Population |
| 14.3.1.3 | Treatment-emergent Adverse Events of Special Interest by System Organ Class and Preferred Term in Descending Frequency | Safety Population |
| 14.3.1.4 | Treatment-emergent Treatment-related Adverse Events by System Organ Class and Preferred Term in Descending Frequency | Safety Population |
| 14.3.1.5 | Serious Adverse Event by System Organ Class and Preferred Term | Safety Population |
| 14.3.1.6 | Treatment-emergent Adverse Event Leading to Study Discontinuation by System Organ Class and Preferred Term | Safety Population |
| 14.3.5 | Extent of Exposure | |
| 14.3.5 | Summary of Study Drug Exposure | Safety Population |
| 14.3.6 | Other Safety Data | |
| 14.3.6.1 | Observed Values and Change from Baseline in Clinical Laboratory Parameters, Hematology | Safety Population |

| Table Number | Table Title | Analysis Set |
|--------------|--|-------------------|
| 14.3.6.2 | Observed Values and Change from Baseline in Clinical Laboratory Parameters, Chemistry | Safety Population |
| 14.3.6.3 | Observed Values and Change from Baseline in Clinical Laboratory Parameters, Urinalysis | Safety Population |
| 14.3.6.4 | Observed Value and Change from Baseline in Clinical Laboratory, Liver Function Tests | Safety Population |
| 14.3.6.5 | Liver Function Abnormalities | Safety Population |
| 14.3.7 | Observed Values and Change from Baseline in ECG Tests | Safety Population |
| 14.3.8 | Observed Values and Change from Baseline in Vital Signs | Safety Population |

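### The SAP counts adverse events that led to leaving the study but not those that led to stopping the drug, so an AE-related drug stop without study exit is not counted by arm

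*SAP*

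**What the plan says.** Three places in the SAP set what is counted.

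- Section 13.2 lists "Subject incidence of TEAEs leading to study discontinuation" by system organ class and preferred term. The matching entry in Appendix C is Table 14.3.1.6, "Treatment-emergent Adverse Event Leading to Study Discontinuation by System Organ Class and Preferred Term".
- Section 9.1 summarises "the number of subjects discontinuing the study, and the primary reason for discontinuation".
- Neither section, and no title in Appendix C, names a summary of study-drug discontinuation, for AEs or for any other reason.

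The protocol separates the two events. Footnote 1 to the Schedule of Assessments covers "Participants who discontinue study treatment and/or the study prior to the scheduled EOT Visit on Day 28" and sends both kinds of subject to an Early Termination Visit. End of Treatment/Early Termination and End of Study are separate columns of that schedule, two weeks apart.

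SAP section 14 describes the termination. Sites were "informed to stop screening and withdraw all subjects from the study", and "Subjects on treatment were notified to stop dosing immediately". SAP 13.1 notes that "12FEB2021 is the date of sponsor notification of sites of study termination for safety reasons".

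**The concern.** How many subjects in each arm stopped the drug because of an AE is a basic tolerability result. It carries extra weight here. Safety is the main thing the SAP still summarises: efficacy is dropped (section 14), PK is reported by the laboratory but not tabulated (section 12), and the termination is attributed to safety.

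A count based on leaving the study answers a different question. The two counts agree only if every AE-related drug stop was also a study exit. The protocol wording does not require that, and the termination gave every remaining subject a second, administrative route out of the study. In a study that section 14 describes as having few randomised subjects, one or two stops missing from the count could change how the table reads.

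**Working it through.** The SAP gives no figure to reproduce on this point. The check is to follow each kind of subject through the planned tables, and then ask whether any other output would show the drug stop.

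**Step 1. Paths through the tables, reading the SAP's words at face value**

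| Path | Table 14.3.1.6 | Disposition (9.1) |
|---|---|---|
| A. Stops drug for an AE and leaves the study for it before 12FEB2021 | Counted | Counted, reason AE |
| B. Stops drug for an AE, stays in the study, withdrawn at termination | Not counted | Counted; reason can be the termination |
| C. Stops drug for an AE, stays, completes Day 42 before termination | Not counted | Not a discontinuation |
| D. On drug with no AE-related stop, told to stop at termination | Not counted | Counted, reason termination |

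Path A is handled correctly. Paths B and C drop out of the AE-related count. In disposition, B can look the same as D, and C looks like an ordinary completer.

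**Step 2. Who could be on path B or C by calendar**

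Inputs: Day 1 is the date of randomisation (SAP section 7), End of Study is Day 42 ±3 (protocol Table 1), and notification was on 12FEB2021 (SAP 13.1).

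- Day 42 falls on 12FEB2021 if Day 1 = 12 Feb 2021 − 41 days = 2 Jan 2021.
- With the +3-day window, Day 45 falls on that date if Day 1 = 12 Feb 2021 − 44 days = 30 Dec 2020.

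Subjects randomised after 2 January 2021 (after 30 December 2020 using the window) could therefore still have been in the study at termination, so path B was open to them. Path C was open to those randomised early enough to finish. The documents do not give randomisation dates, so neither group can be sized.

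**Step 3. Does the exposure table fill the gap?**

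SAP 13.1 has one branch for "Subjects who prematurely discontinue prior to Day 28/EOT", and its day count runs to 12FEB2021 rather than to the subject's own last dose. I read the denominator as 2 × days, in line with the completer formula.

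Assumed example: first dose 16 Jan 2021, which gives 28 days to 12FEB2021 and an expected 2 × 28 = 56 tablets. The subject takes every dose until she stops.

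- Stop after Day 7: 14/56 = 0.25
- Stop after Day 10: 20/56 = 0.36
- Stop after Day 14: 28/56 = 0.50

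A subject who missed scattered doses but used the same number of tablets gives the same values. With her own last-dose date in the denominator, each ratio would be 1.00 (for example 14/14). The exposure summary therefore cannot tell an early stop from poor compliance, and it carries no reason.

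**Step 4. Other outputs**

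The overall TEAE summary (Table 14.3.1.1) and the AE listing (16.2.7) might carry action taken with study drug, but the SAP specifies the content of neither. A listing would allow the cases to be recovered one by one, but it would not give a count by arm.

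**The case against.** The strongest case against rests on four points.

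- **Such subjects may not exist.** Only the protocol synopsis and schedule are available. Footnote 1 sends both kinds of subject to the same Early Termination Visit, and nothing supplied says that a subject who stopped the drug early went on into follow-up. SAP 13.1 itself uses a single term for early discontinuation. This stands as a limit on size. It does not remove the gap, because the footnote's wording allows either event without the other.
- **The SAP does not say how a TEAE is flagged as leading to study discontinuation.** The flag may come from an eSource field in which sites used the two terms interchangeably. This also stands, and it is why the point is conditional. A sentence in 13.2 would settle it.
- **The events are not lost.** Every TEAE remains in the tables by system organ class and preferred term, and in the special-interest, treatment-related and serious summaries where it qualifies. Liver abnormalities have their own table, 14.3.6.5. AEs and disposition are also listed by subject. This is correct: what may be missing is one classification of reported events, not the events themselves.
- **The protocol's safety endpoints do not name drug discontinuation for AEs.** They name incidence and severity of AEs, so no promised endpoint is broken.

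A reader might go further and infer that neither table can tell stops caused by the drug from stops caused by the sponsor. The documents do not support that. Section 9.1 tabulates a primary reason by arm, which can separate exits for AEs from exits for the termination. The SAP does not list the reason categories, and nothing suggests that termination is not among them. Only a drug stop without study exit escapes.

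**Conclusion.** The point holds in a narrow form. On the SAP's wording, an AE that led to stopping the drug but not to leaving the study falls outside the only AE-related discontinuation count, and no other planned table is specified to supply it by arm.

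The number of subjects affected cannot be computed: the documents give no randomised count, no discontinuation counts and no stop dates. It is nil if every AE-related drug stop was also a study exit, and at most the number of subjects who stopped the drug for an AE and stayed in the study. A reader might infer that stops were in fact hidden in this trial, but no document shows that such a subject exists.

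The conclusion assumes that study discontinuation in 13.2 and 9.1 means leaving the study, as distinct from stopping treatment in the protocol's footnote. This is a cheap improvement to the reporting, not a flaw that invalidates the safety analysis.

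**What to change.** - **SAP 13.2 and Table 14.3.1.6:** add subject incidence of TEAEs leading to discontinuation of study drug, by treatment group, and keep the study-discontinuation count beside it. State which data field or matching rule defines each.
- **SAP 9.1 and Table 14.1.1:** add treatment discontinuation with its own primary reason, separate from study discontinuation, and show sponsor termination as a distinct reason.

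Both changes affect reporting only and touch no clinical rule. The cost is wording in two sections and a few extra table rows. If the eSource forms have no field for action taken with study drug, drug-stop dates would have to be matched by hand to AE dates, for what should be a few subjects. That matching involves judgement, so its rule should be written down in the SAP.

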13.3 Clinical Laboratory Evaluation

Laboratory samples will be analyzed by a central laboratory. The central laboratory will provide normal reference ranges for the laboratory results and a flag for all abnormal values.

Laboratory safety parameters for hematology, serum chemistry, and urinalysis will be summarized descriptively at baseline and at each post-baseline time point (Day 14, 28/EOT, and Day 42/EOS) and will include change from baseline. Baseline is defined as the last non-missing value prior to first dose of study drug.

Laboratory safety parameters for liver function tests (LFTs) will be summarized descriptively at baseline and at each post-baseline time point (Day 7, Day 14, 28/EOT, and Day 42/EOS) and will include frequency count and percent for each test category. Potential Hy's Law cases will be identified using the common criteria of 2x upper limit normal (ULN) total bilirubin concurrent with 3x ULN aspartate aminotransferase (AST) or alanine aminotransferase (ALT) (whichever is higher) when aspartate aminotransferase (ALP) is < 2x ULN.

Categorical parameters for urinalysis laboratory results will not be summarized but will be presented in a data listing.

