**Table 1: Schedule of Assessments**

	Screening Period		Treatment Period			Follow-Up
	Screening	Run-In	Baseline	Study Visit	End of Treatment/ Early Termination 	End of Study
Study Day	-30 to -15	-14 to -1	1 ±2	7 ±2	14 ±2	28±3
Study Week	-4 to -2	-2 to -1		1	2	4
Visit Location	Clinic	Phone option	Clinic	At home option	At home option	Clinic
Events						
Informed consent form signed	X					
Review inclusion/exclusion criteria & medical history	X		X			
Demographics	X					
Physical examination 	X		X			X
Randomization			X			
Height and weight 	X		X			X
Concomitant medications	X	X	X	X	X	X
Adverse event monitoring	X	X	X	X	X	X
HIV and hepatitis tests	X					
Pregnancy test (urine)	X		X			X
Drugs of abuse screening 	X		X			X
Vital signs 	X		X	X	X	X
12-lead ECG	X		X			X
Hematology	X		X		X	X
Total serum chemistry 	X		X		X	X
LFTs only				X		
Urinalysis	X		X		X	X
COVID-19 testing 	X		X		X	X
E2, SHBG, LH, FSH 	X 		X	X	X	X
Endometrial biopsy 						X
Transvaginal ultrasound 		X				X
Mammogram 		X				

	Screening Period		Treatment Period			Follow-Up	
	Screening	Run-In	Baseline	Study Visit	End of Treatment/ Early Termination 	End of Study	
Study Day	-30 to -15	-14 to -1	1 ±2	7 ±2	14 ±2	28±3	42±3
Study Week	-4 to -2	-2 to -1		1	2	4	6
Visit Location	Clinic	Phone option	Clinic	At home option	At home option	Clinic	At home option
Events							
Pap smear and HPV testing 	X						
Plasma PK collection 				X		X	
Dispensing of medication			X				
Drug accountability and compliance check				X	X	X	
Dosing of medication in clinic 			X			X	
Recording of VMS frequency/severity in daily HF eDiary 							→
Recording of body temperature in daily eDiary 							→
HFRDIS			X		X	X	
ISI			X			X	

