7. NOTATION OF TREATMENT GROUPS AND VISITS

Notation of treatment groups

The following notation of **treatment groups** will be used throughout the report:

| Full notation (as used in the study protocol) | Notation as used throughout all tables, listings and figures |
|--|---|
| 20 mg SJX-653 | 20 mg SJX-653 |
| Placebo | Placebo |

Visit terminology

| Week | Day | Visit | Notation as used throughout all tables, listings and figures |
|--------------------|---------------|----------------|---|
| Week -4 through -1 | Day -30 to -1 | V1 (Screening) | Screening/Run-In |
| Week 1 | Day 1 | V2 (Baseline) | Baseline |
| Week 1 | Day 2 to 7 | V3 | Day 7 |
| Week 2 | Day 8 to 14 | V4 | Day 14 |
| Week 4 | Day 15 to 28 | V5 | Day 28 / EOT |
| Week 6 | Day 29 to 42 | V6 | Day 42 / EOS |

Days are measured from date of randomization. Study days corresponding to measurements are calculated as:

- Assessment date – date of randomization + 1, if assessment date is on or after the date of randomization.
- Assessment date – date of randomization, if measurement date is before the date of randomization.

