13.5 Vital Signs

Vital signs will be summarized using descriptive statistics at baseline and at each post-baseline time point (Day 7, 14, 28/EOT, 42/EOS) and will include change from baseline. Baseline is defined as the last non-missing value prior to first dose of study drug.

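### After the 12FEB2021 safety stop, SAP 13.3 and 13.5 summarise laboratory, liver and vital-sign results only by scheduled visit, so post-drug closing results can be pooled with completers' on-drug results

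*SAP*

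**What the plan says.** **The stop.** The note in SAP 13.1 records that "12FEB2021 is the date of sponsor notification of sites of study termination for safety reasons". SAP 14 adds that sites were to withdraw everyone and that "Subjects on treatment were notified to stop dosing immediately".

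**The tables.** SAP 13.3 summarises liver tests "at each post-baseline time point (Day 7, Day 14, 28/EOT, and Day 42/EOS"). Haematology, chemistry and urinalysis use the same visits without Day 7. SAP 13.5 summarises vital signs "at each post-baseline time point (Day 7, 14, 28/EOT, 42/EOS").

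**The visit labels.** The visit table in SAP 7 contains rows such as "Week 4 | Day 15 to 28 | V5 | Day 28 / EOT" and states that "Days are measured from date of randomization". It does not say whether the visit name or the day span decides where a result is placed.

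**The closing visit.** Protocol Table 1 has one column headed "End of Treatment/ Early Termination". Footnote 1 sends women who stop treatment or the study before the EOT visit to an Early Termination visit and says: "The procedures at this Early Termination Visit will be the same as those specified for EOT". Under footnote 16, women who reach EOT are dosed in the clinic that day.

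**The concern.** The SAP was adapted to the stop in other places. Efficacy was dropped, only a safety population was kept, and SAP 13.1 gives exposure one formula for women who completed Day 28/EOT and another, ending on 12FEB2021, for those who did not. That distinction was not carried into SAP 13.3 or 13.5.

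For a completer, the visit columns roughly separate on-drug (Day 28) from off-drug (Day 42). For a woman whose dosing was cut short, they need not. Her closing visit may come after her last dose and still be tabulated beside on-drug values.

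In a trial stopped for safety, readers will want to know whether a test changed on drug, and whether it recovered or first became abnormal after the last dose. SAP 14 says that few women were randomised, so a handful of post-drug values could move a column.

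**Working it through.** The plan states no figure on this point, so there is none to reproduce. The check sets the rules side by side and works out the dates.

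**1. Was the SAP written with the stop known?** The SAP date is 02APR2021 (page header) and the stop is 12FEB2021 (SAP 13.1). From 12FEB to 28FEB is 16 days, March has 31, and two more reach 02APR: 16 + 31 + 2 = 49 days.

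**2. Who could have been interrupted?** SAP 7 defines study day as date minus randomisation date plus 1. Protocol Table 1 allows EOT on Day 28 ± 3, that is Days 25 to 31.

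- Randomised 12FEB2021: 0 + 1 = Day 1 at the stop.
- Randomised 20JAN2021: 23 + 1 = Day 24, the last day before EOT was permitted.
- Randomised 19JAN2021: 24 + 1 = Day 25.
- Randomised 13JAN2021: 30 + 1 = Day 31.

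Any woman randomised from 20JAN to 12FEB2021 had her treatment cut short before a permitted EOT visit, unless she had already left. Those randomised from 13JAN to 19JAN2021 may or may not have had EOT. These are dates; the documents do not say how many women fall in either range.

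**3. Where does a closing result go?** Two rules are open.

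- *By visit name.* Early Termination shares the EOT column, so the result goes under Day 28/EOT whatever its study day.
- *By the SAP 7 day span.* The column depends on the study day of the visit:

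| Study day of closing visit | Column |
|---|---|
| 2 to 7 | Day 7 |
| 8 to 14 | Day 14 |
| 15 to 28 | Day 28/EOT |
| 29 to 42 | Day 42/EOS |

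An invented example: a woman is randomised on 08FEB2021, takes her last dose on 12FEB2021 and has her closing visit on 15FEB2021.

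- Study day at the stop: 12 − 8 + 1 = 5.
- Study day at the closing visit: 15 − 8 + 1 = 8.
- Days since last dose: 15 − 12 = 3.
- Column by visit name: Day 28/EOT. Column by day span: Day 14.

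Under either rule her result joins values from women still on drug, and nothing marks it as taken after the last dose. A completer at EOT, dosed in the clinic that day, is 0 days from last dose.

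**4. The day spans do not match the visit windows.** The protocol allows EOT up to Day 31, but the SAP 7 span ends at Day 28. By day span, a completer's on-drug EOT result on Days 29 to 31 would fall under Day 42/EOS. The spans may therefore be meant only as terminology, but the SAP does not say so.

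**5. Does anything else separate the two states?**

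| Place | What it offers | What it lacks |
|---|---|---|
| SAP 13.3, 13.5 | Visit summaries by arm | An on-treatment flag or a separate Early Termination column |
| SAP 13.3, Hy's Law | A screen not tied to a visit | Anything below that threshold |
| Appendix C, Table 14.3.6.5 | Liver abnormalities | A stated layout |
| Appendix A | Listings sorted by subject, visit and date/time | Days since last dose |
| Appendix C, index of 16.2 | Laboratory and vital-sign listings | A dosing or exposure listing |

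Appendix C permits minor index changes without a SAP amendment, so a dosing listing could still be added.

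**The case against.** The strongest case against runs as follows.

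- **Visit summaries follow the protocol schedule.** Nothing in the documents requires tables by time since last dose. That is correct, but the schedule was written for four weeks of dosing, and the SAP was written knowing that dosing had been cut short.
- **No arm is favoured by design.** Safety analysis is descriptive, randomisation was 1:1 and the stop applied to both arms, so interruption should affect both similarly in expectation. This stands. What remains is that post-drug values mixed into the active-arm column can dilute a change that reverses after dosing, or make a late one look like an on-drug one.
- **Individual data will show onset and recovery.** With few women, dated listings are a natural place to look, and days since the stop can be approximated from 12FEB2021. This stands in part: the plan does not ask for that step, and no dosing listing is named.
- **The harm depends on facts not given.** With a short gap to the closing visit, or a long half-life, a closing result may in effect be on-drug. This stands, and it is why no size can be attached.
- **Some documents are not in view.** Table shells, the data management plan and the DMC charter might hold a labelling rule. That is possible, but the SAP is where a reader would expect it.

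A reader might count days from the stop to each woman's nominal Day 28 or Day 42 visit and quote those as the gap since last dose. The documents do not support this. SAP 14 has all subjects withdrawn, and Protocol Table 1 sends them to an Early Termination visit, so later nominal visits cannot be assumed.

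**Conclusion.** The point holds as a weakness of the stated summaries. Following SAP 13.3 and 13.5 as written, closing results taken after the last dose in interrupted women can be pooled with completers' on-drug results under Day 28/EOT, or enter another visit column if the SAP 7 spans decide the label. Its size is unknown, because the number of women interrupted, the time from last dose to closing visit and the half-life are not given. The conclusion assumes that at least some interrupted women had a closing visit after their last dose, as the protocol asks. The listings, the Hy's Law screen and Table 14.3.6.5 limit the harm. It is a cheap improvement, and it does not concern adverse events.

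Two stronger readings should be resisted.

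- A reader might infer that most such results land under Day 28/EOT. That is certain only if visit name decides. If day spans decide, and last doses are assumed to be evenly spread over Days 1 to 27 with a closing visit 0 to 14 days later, the share is 13/27 to 14/27, or 48% to 52%. At a 14-day gap the remaining 13/27 (48%) fall under Day 42/EOS. The even spread is itself undocumented.
- A reader might infer from the Hy's Law screen and the hepatology member of the DMC that a liver signal stopped the trial. The documents say only that it was stopped for safety reasons.

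**What to change.** In SAP 13.3 and 13.5:

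1. State how Early Termination and unscheduled results are assigned to a visit: by visit name or by study-day span.
2. Flag each post-baseline result as on-treatment or post-treatment by last-dose date, with a cut-off that the sponsor sets from the half-life. Where the last-dose date is missing for a woman on treatment at the stop, use 12FEB2021 as a stated approximation. Summarise post-treatment results of interrupted women separately from on-treatment Day 28/EOT results.
3. Show days since last dose in the laboratory and vital-sign listings.

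The cost is a few sentences, one derived flag, a split of existing summaries and one listing column, all from data already collected. No new visits are needed. The drawbacks are slight extra programming and sparse cells in the post-treatment summaries.
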